15.3 Adverse Events

Reporting will be done for SAF.

Adverse events are events that are reported with a start date on or after the end of clinical trial + 1 day [Registry Day 1].

AEs collected in PREMIERE either from AEs CRF Pages (AE dataset) or New Diagnoses CRF Pages (CE dataset) will be included.

Seriousness is not collected for events in the New Diagnoses CRF Pages. Seriousness will not be imputed and therefore these diagnoses will not be included in serious or non-serious AE tables.

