## **8.5.1                      Definitions**

### **8.5.1.1                  Adverse Events**

An AE is defined as any untoward medical occurrence in the form of signs, symptoms, abnormal laboratory findings, or disease that emerges or worsens relative to study baseline.

When reporting an abnormal laboratory finding, a clinical diagnosis should be recorded rather than the abnormal value itself, if this is available. For example, record “anemia” rather than “decreased red blood cell count” or “hemoglobin = 10.5 g/dL”.

AEs may include the following types of occurrences:

- Medical experiences, such as injury, surgery, accidents, or illnesses, and significant abnormalities in clinical laboratory values, psychological testing, or physical examination findings.

In cases of surgical or diagnostic procedures, the condition/illness leading to such a procedure is considered as the AE rather than the procedure itself.

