In this protocol, any adverse pregnancy outcome (e.g., spontaneous abortion, fetal death in utero, ectopic pregnancy, chronic fetal distress, stillbirth, neonatal death, or prematurity-related complication more than is typical for prematurity) should be considered serious. Serious adverse events occurring to offspring of a female subject should also be reported and evaluated as SAEs.

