### 8.5.1.5 Definition of the Adverse Event Reporting Period

SAEs are documented from the day informed consent is signed until the subject's last interview (end of study). Beyond that date, ongoing SAEs, including persistent Grade 3 or Grade 4 lymphopenia, and pregnancies will be followed up until event resolution/stabilization or pregnancy outcome is known by the Global Drug Safety Department. Offspring of female subject born during registry participation who are less than 1 year old at the end of the registry will be followed up until 1 year of age by the Global Drug Safety Department.

If PRP/reporter becomes aware of a SAE, which occurred during the lag interval period, but was not reported within a prior cladribine trial, s/he should report this event to the Global Drug Safety department.

If a subject is documented as lost-to follow-up, ongoing SAEs will not be followed up.

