#### 8.5.3.1                      Pregnancy and In Utero Drug Exposure

All pregnancies with an estimated conception date during the period defined in Section 8.5.1.5 must be recorded by convention in the AE page/section of the CRF. The PRP/reporter must notify the Sponsor in an expedited manner of any pregnancy using the Pregnancy Report Form, which must be transmitted according to the same process as described for SAE reporting in Section 8.5.3.

Investigators must actively follow up, document and report on the outcome of all of these pregnancies, even if the subjects are withdrawn from the registry. Offspring of female subjects will be followed-up for one year after delivery or until the registry end, whichever occurs first.

The Investigator must notify the Sponsor of the outcomes using the Pregnancy Report Form, and in case of abnormal outcome, the GDS Alert Report Form when the subject sustains an event and the GDS Parent-Child/Fetus Adverse Event Report Form when the child/fetus sustains an event).

Any abnormal outcome must be reported in an expedited manner as described in Section 8.5.3, while normal outcomes must be reported within 45 days from delivery.

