15.3.1 All Adverse Events

All adverse events will be summarized following statistics described in section 15.1.1.

Clinical trial.gov and EudraCT -requirements

In addition, a summary table will be provided for non-serious adverse events by SOC and PT per treatment group excluding SAEs applying

- frequency threshold of 5% based on crude incidence in either group

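### Uncomplicated pregnancies are recorded on the AE page as a convention, and SAP 15.3 does not remove them from the all-AE and non-serious AE tables

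*SAP*

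**What the plan says.** Protocol 8.5.3.1 states that all pregnancies with an estimated conception date in the reporting period "must be recorded by convention in the AE page/section of the CRF". Protocol 8.5.1.5 runs that period from consent to the last interview. The rule does not depend on outcome: the same section gives normal outcomes their own, slower reporting timeline. Protocol 8.5.1.1 defines an adverse event as "any untoward medical occurrence in the form of signs, symptoms, abnormal laboratory findings, or disease", and Protocol 8.5.1.3 makes only adverse pregnancy outcomes serious.

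SAP 15.3 uses a working definition based on date and source: "Adverse events are events that are reported with a start date on or after the end of clinical trial + 1 day". It then adds that "AEs collected in PREMIERE either from AEs CRF Pages (AE dataset) or New Diagnoses CRF Pages (CE dataset) will be included". It names no excluded terms. SAP 15.3.1 summarises all of these events and adds a non-serious table by SOC and PT for public posting, with a "frequency threshold of 5% based on crude incidence in either group".

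SAP 15.2 recognises that pregnancies sit in the AE data. It screens AE terms against the pregnancy SMQ (Appendix 18.1) and records in Appendix 18.2 which ones qualify as pregnancies. That classification serves the secondary endpoint, and 15.3 does not refer to it.

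On offspring, Protocol 8.5.1.3 says "Serious adverse events occurring to offspring of a female subject should also be reported and evaluated as SAEs". Protocol 9.2.2 promises a descriptive summary of important health conditions in the offspring. SAP 15.2 plans infant status, birth defects and listings.

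**The concern.** The protocol uses the AE page as a place to log pregnancies, while the SAP treats presence on that page, with a qualifying start date, as what makes something an adverse event. Following both texts as written, a healthy pregnancy becomes an adverse event of the subject.

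Three features give this some weight:

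- The current protocol asks only for SAEs and for AEs in two SOCs. A normal pregnancy is neither, so it reaches the AE tables solely through the convention, and in a small non-serious pool it would be conspicuous.
- Crude incidence divides by all subjects of both sexes, and the SAP has added a never-exposed reference group. If the two groups differ in sex or age mix, pregnancy records could show up as a difference in adverse events. The documents give no group composition, so this is a possibility only.
- The non-serious table is intended for public registries.

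**Working it through.** **Does any rule remove the records?** SAP 15.3 applies a start-date filter and names two source datasets. SAP 15.2 identifies pregnancies for its own endpoint. SAP Section 7 (Table 1) lists no change on this point. No visible text takes pregnancy records out of the 15.3 tables. The content of Appendix 18.2 could not be checked; 15.2 describes it as deciding what is a pregnancy, not as an AE-table exclusion.

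**Which outputs are touched?**

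- SADR (SAP 15.1.1) requires serious and probably or possibly related: not touched.
- The two SOC endpoints (15.1.2, 15.1.3) select by SOC: not touched.
- Lymphopenia (15.1.4) uses lymphocyte counts and a CRF tick box: not touched.
- All AEs and non-serious AEs (15.3.1): touched.

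**Size.** The only pregnancy frequency in the documents is CLARITY's (Protocol 3). It is internally consistent: by arm 6 + 7 + 11 = 24; by timing 6 + 17 + 1 = 24; by outcome 5 + 13 + 1 + 4 + 1 = 24 pregnancies, in 23 women.

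Inputs: 23 of 898 women; 898 women among 1326 subjects; 1161 full participants (SAP Section 7), slightly more than the SAF because DDI subjects are excluded from it. Assumed: 2 years of CLARITY follow-up, 4 to 6 registry years, and the CLARITY sex mix.

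- Women with a pregnancy in CLARITY: 23/898 = 2.56%.
- Share of women: 898/1326 = 67.7%; 0.677 × 1161 = 786 women.
- Over 4 to 6 years: 2.56% × 2 to 2.56% × 3 = 5.1% to 7.7% of women, or 40 to 60 women.
- As a share of all subjects: 40/1161 to 60/1161 = 3.5% to 5.2%.

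A constant-rate model, with 1.84 to 2.0 years assumed for CLARITY, gives 3.4% to 3.7% at 4 years and 5.1% to 5.5% at 6 years.

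These figures count every pregnancy. Taking CLARITY's 4 miscarriages, 1 ectopic pregnancy and 1 choriocarcinoma termination as serious leaves 18 of 24:

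- 40 × 18/24 to 60 × 18/24 = 30 to 45 women, or 2.6% to 3.9% of 1161.
- Counting only full-term normal live births (5 of 24): about 8 to 12 women, or 0.7% to 1.1%.

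**The 5% threshold.** It corresponds to 59 of 1161 subjects, or 12 to 18 subjects in an assumed never-exposed group of 232 to 348 (20% to 30%). With every record under one PT, the exact binomial chance that either group reaches 5% is about 2% to 5% at a true incidence of 3%, 23% to 27% at 4%, and 74% at 5%.

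**Sensitivity.** CLARITY required contraception, so the registry rate may be higher. At twice the CLARITY rate and 4 years, any pregnancy reaches 6.7% to 7.2%; times 18/24 that is 5.0% to 5.4%, around the threshold if all records share one PT.

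**The case against.** The strongest reply is that this touches only descriptive tables. No primary endpoint moves, no inference is planned, and the all-AE results are broken down to PT, so a pregnancy row would be visible and a reader could set it aside. That stands, and it limits the importance of the point. It does not make the count right: the overall number of subjects with at least one AE cannot be corrected from the PT rows.

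A reader might infer that pregnancy will be posted as a common non-serious adverse event. The documents do not support that. The 3.5% to 5.2% includes pregnancies whose outcomes are serious, the threshold applies by PT, and the SMQ list separates pregnancy, unintended pregnancy, pregnancy on contraceptive and pregnancy of partner, among others. The 4 to 6 years may also be generous: follow-up stops at 8 years from first trial enrolment at the latest, and the trial, any extension and the lag before consent all use up part of that.

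A reader might also infer that appearing under both 15.2 and 15.3 is an error in itself. It is not. These are separate outputs that are never added together, and a malignancy may likewise appear in several. The fault is only that an event which is not untoward is counted as an adverse event.

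Finally, a reader might infer that infants' events will be attributed to their mothers. No text says that child events are entered under the mother's number. The protocol has a separate parent-child/fetus form and separate neonatal and offspring questionnaires. What remains is that the SAP does not state how such a record would be handled.

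**Conclusion.** The gap is real and narrow. Under the texts as written, uncomplicated pregnancies enter the all-AE tables and the non-serious pool although they fall outside the protocol's AE definition. Partner pregnancies would enter too if sites record them on the AE page. The three primary endpoints are unaffected.

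The size cannot be fixed from the documents. At the CLARITY rate, under the assumptions above, roughly 3.5% to 5.2% of subjects would have any pregnancy, and about 2.6% to 3.9% one without an outcome treated as serious. The rise in all-AE incidence would be smaller still, because some of these subjects have another AE anyway. Crossing 5% is possible but unlikely at that rate. It becomes more plausible if pregnancy is appreciably commoner without a contraception requirement, and the CLARITY mix of outcomes may not carry over either.

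On offspring, the supported point is an undeclared shortfall: the protocol promises a summary of important health conditions, SAP 15.2 covers only part of it, and the SAP's table of changes does not mention this.

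**What to change.** In SAP 15.3, exclude from the all-AE and non-serious AE tables those AE-page records that are pregnancy only, including pregnancy of a partner, and report them only under 15.2. Identify them with the 15.2 term classification together with the recorded pregnancy outcome. A term list alone may not show whether a given pregnancy ended normally. Keep pregnancy complications and adverse outcomes in the AE and SAE tables, and say explicitly where elective terminations fall, since Protocol 8.5.1.3 does not name them among its examples of serious outcomes.

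State that any AE-page record concerning a child is not counted in the mother's incidence. Add to 15.2 a descriptive summary of important health conditions in the offspring at birth, 6 months and 1 year, matching Protocol 9.2.2 and Appendix II.

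The cost is a few sentences, one table and a small amount of record-level linkage, with no new data. All-AE totals will differ slightly from the two intermediate synoptic reports in SAP 6.1; a footnote can explain this.

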### **8.5.1.3                  Serious Adverse Events**

Any SAE requires expedited reporting to the Sponsor’s (GDS) Global Drug Safety Department.

A serious adverse event (SAE) is defined as any adverse event occurring at any dose that results in any of the following outcomes, which are seriousness criteria:

- Results in death. In case of a fatality, the cause of death is considered as the SAE, and the death is its outcome
- Is life-threatening. The term “life-threatening” in this definition refers to an event in which the subject is at risk of death at the time of the event; it does not refer to an event that hypothetically might have caused death if it were more severe.
- Requires in-patient hospitalization or prolongation of existing hospitalization.
- Results in persistent or significant disability/incapacity.
- Is a congenital anomaly/birth defect.
- Is otherwise considered as medically important.

Important medical events that may not result in death, be life-threatening, or require hospitalization may be considered a serious adverse drug experience when, based upon appropriate medical judgment, they may jeopardize the patient or subject and may require medical or surgical intervention to prevent one of the outcomes listed in this definition. Examples of such medical events include allergic bronchospasm requiring intensive treatment in an emergency room or at home, blood dyscrasias or convulsions that do not result in patient hospitalization, or the development of drug dependency or drug abuse.

The treating physician or other relevant concerned health care provider will be asked to assess the relationship of the SAEs to cladribine using the following definitions:

- **Probable:** A causal relationship is clinically/biologically highly plausible, and there is a correlation between the onset of the SAE and administration of cladribine, and between withdrawal of cladribine and resolution of the SAE.
- **Possible:** A causal relationship is clinically/biologically plausible and there is a correlation between the onset of the SAE and administration of cladribine.
- **Unlikely:** A causal relationship is improbable, and another documented cause of the SAE is most plausible.
- **Unrelated:** A causal relationship can be definitively excluded, and another documented cause of the SAE is most plausible.

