#### **SAEs of particular interest**

Any malignant neoplasia, including non-melanoma skin cancer as well as all serious infections should be considered as a medically significant adverse event and reported to the Sponsor using an SAE Report Form with all related information.

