15.3.2 Serious Adverse Events

Serious adverse events will be presented following statistics described in section 15.1.1

Clinical trial.gov and EudraCT -requirements

In addition, a summary table will be provided for serious adverse events by SOC and PT per treatment group.

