15.5.1 AESI= Infections

Reporting will be regrouped into the 7 following AESI categories.

- AESI = Infections and Infestations

AESI = Infections and infestations is defined by any event belonging to the MedDRA SOC = Infections and Infestations.

- AESI = Severe Infections

AESI = Severe Infections is a custom grouping defined by any serious or severe event belonging to the MedDRA SOC = Infections and Infestations.

Data Handling

[REDACTED]

[REDACTED]

Adverse events collected under the New Diagnosis pages (PREMIERE eCRF only) does not have characteristics for severity being collected. However, AEs collected under the category “Other **severe** infections” will be considered for the definition of the AESI = Severe Infections.

- AESI = Herpetic infections

AESI = Herpetic infections is a custom grouping defined by any events from MedDRA HLT = Herpes viral infections.

- AESI = Opportunistic infections

The medical concept “opportunistic infections (including tuberculosis and PML)” is a custom grouping based on medical assessment. It includes MedDRA Preferred Terms (PTs) associated to viral, protozoal and bacterial infections as well as PTs associated to fungal infections with the exclusion of mucocutaneous and cutaneous fungal infections. Infections as provided by the US Centers of Disease Control (1993 revision) and in the Guidelines for the Prevention and Treatment of Opportunistic Infections in HIV-Infected Adults and Adolescents, <http://aidsinfo.nih.gov/guidelines> are included. PTs pertaining to the HLT ‘Herpes viral infections’ are not included.

This definition will be shortened in the tables footnote to read:

AESI = Opportunistic Infections is based on respective lists available in the context of HIV infections. It includes MedDRA preferred terms (PTs) associated to viral, fungal, protozoal and bacterial infections. PTs pertaining to the HLT ‘Herpes viral infections’ are not included.

The MedDRA terms that will be selected are listed in Appendix 18.3.

- AESI = Herpes zoster infections

AESI = Herpes zoster infections is a custom grouping defined by PTs with the term 'herpes zoster'.

The PTs that will be selected are listed in Appendix 18.4.

- AESI = PML

AESI = PML is a custom grouping defined by any events from MedDRA HLT = Polyomavirus infection.

- AESI = Tuberculosis

AESI = Tuberculosis is a custom grouping defined by any events from MedDRA HLT = Tuberculous infections.

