15.5.2 AESI = Malignancies

The AESI Malignancies is a custom query using the following process:

All PTs from MedDRA SMQ (SMQ code 20000091) labelled “Malignant or unspecified tumours” are identified (see Appendix 18.5). For this SMQ, there are no broad terms available. The obtained list is reviewed, and an adjudicated decision is made with documented justifications which events qualify as malignancies. These classifications are documented with reasons in Appendix 18.6 and read into the programs for calculations.

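### SAP 15.3 keeps every New Diagnoses page event out of the serious AE tables, although the protocol makes any malignancy serious by diagnosis; a malignancy recorded only on those pages would be missing from the serious rows (number not given, possibly zero)

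*SAP*

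**What the plan says.** SAP 15.3 takes adverse events from two sources: the AE pages (AE dataset) and the New Diagnoses pages (CE dataset). It notes that the second source has no seriousness field and concludes: "Seriousness will not be imputed and therefore these diagnoses will not be included in serious or non-serious AE tables". The section makes no exception for any type of diagnosis. The rule agrees with the general no-imputation statements in SAP 9.12 and protocol 9.3.1.

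Protocol 8.5.1.3, under its heading on SAEs of particular interest, says: "Any malignant neoplasia, including non-melanoma skin cancer as well as all serious infections should be considered as a medically significant adverse event". The same sentence sends these events to the sponsor on an SAE form. The seriousness criteria in 8.5.1.3 include: "Is otherwise considered as medically important".

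Two other SAP sections bear on the point.

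- Section 15.5.1 meets a similar gap for infections: "Adverse events collected under the New Diagnosis pages (PREMIERE eCRF only) does not have characteristics for severity being collected". It nevertheless says that events under the CE category Other severe infections "will be considered for the definition of the AESI = Severe Infections".
- Section 15.5.2 sets up a reviewed list of malignancy terms: "The obtained list is reviewed, and an adjudicated decision is made with documented justifications which events qualify as malignancies".

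**The concern.** The SAP handles every CE event as having unknown seriousness. That is reasonable for most diagnoses. For a malignancy, the protocol has already settled the question. Applying a protocol definition to a known diagnosis is classification, and a ban on imputing missing values does not forbid it.

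The exclusion can only lower serious counts. Malignancy is named in the registry's first primary objective, and the protocol background describes the earlier relative risk (2.31, 95% CI 0.27 to 19.80) as unstable. Serious malignancy counts will be read closely, and they may be small. The SAP discloses the rule and its reason, but the visible text specifies no footnote and no count of malignancies that it removes. A reader of the tables could not tell whether that number is zero.

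**Working it through.** The plan gives no figure on this point to reproduce. The check is a comparison of texts, followed by a bound on the effect.

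**Step 1: is a malignancy serious under the protocol?** The protocol calls any malignant neoplasm medically significant, under a heading about SAEs, and requires an SAE form. Medical importance is a listed criterion. The adjectives differ (significant, important), but the heading and the reporting route leave no other sensible reading. The same argument does not extend to infections: the protocol sentence names only infections that are already serious, so an infection diagnosis alone does not settle the matter.

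**Step 2: which outputs would omit a CE-only malignancy?**

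| Output | Effect |
|---|---|
| SAE tables, 15.3.2, including the registry-posting table ("a summary table will be provided for serious adverse events by SOC and PT per treatment group") | omitted |
| Serious row, Neoplasms SOC (15.1.3 takes over the 15.1.2 analyses, which repeat the 15.1.1 statistics, including those for serious AEs) | omitted |
| Serious row, AESI Malignancies (15.5) | omitted |
| All-event totals: all AEs (15.3.1), Neoplasms SOC, AESI Malignancies | still counted |
| Primary SADR endpoint (15.1.1) | not shown: needs a probable or possible relationship as well, and the documents do not say whether CE pages record one |

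**Step 3: how much can one case matter?** The formula is crude incidence = n/N × 100, with exact Clopper-Pearson limits, as in SAP 15.1.1. The largest change per subject is 1/N. It is zero if the subject already has another serious event in that row.

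For the total column, N = 1161 full participants (SAP Table 1). The Safety Analysis Population is smaller by the drug-interaction study subjects, whose number is not given. 1/1161 = 0.086 percentage points.

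Treatment-group sizes are not given. The values 200, 400 and 900 below are assumptions.

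| N | 0 events: 95% CI | 1 event: % (95% CI) |
|---|---|---|
| 1161 | 0 to 0.317% | 0.086 (0.002 to 0.479) |
| 200 (assumed) | 0 to 1.828% | 0.500 (0.013 to 2.754) |
| 400 (assumed) | 0 to 0.918% | 0.250 (0.006 to 1.385) |
| 900 (assumed) | 0 to 0.409% | 0.111 (0.003 to 0.618) |

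If 10 subjects were already counted at N = 1161 (an assumption), one more moves the row from 0.86% (0.41 to 1.58) to 0.95% (0.47 to 1.69).

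**The case against.** The strongest reply is that a CE-only malignancy requires a reporting failure. Protocol 8.5.1.3 sends every malignancy to an SAE form, 8.5.2 requires all SAEs and all Neoplasms SOC events in the CRF, and 8.5.3 requires the form and the CRF to agree. With full compliance the exclusion removes nothing. This stands as a limit on the count. It does not remove the conflict, because the visible SAP text specifies no reconciliation of CE events against SAE reports, and the general query resolution in SAP 6.2 does not override an explicit exclusion.

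It can also be said that the protocol sentence instructs the reporter and does not tell the statistician to fill a field that was never collected. That is a fair distinction, but the sentence applies to any malignancy, and the seriousness definition is the one behind the SAE tables.

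Three further points stand in part.

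- The infection precedent in 15.5.1 is only partial: a reporter who chose a category with severe in its name had already recorded severity. Nothing shows a CE malignancy category that does the same for seriousness.
- Appendix 18.6 and some data-handling text in 15.5.1 are not visible, so the absence of a matching rule cannot be fully confirmed.
- The protocol does not describe the New Diagnoses pages, so it is not known when they were in use.

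A reader might infer that such malignancies are wrongly lost from both registry-posting tables. The second is described as follows: "a summary table will be provided for non-serious adverse events by SOC and PT per treatment group". That table is not a concern. A serious event does not belong in it, and its 5% threshold would need 0.05 × 200 = 10 to 0.05 × 900 = 45 subjects with the same term at the assumed group sizes.

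**Conclusion.** The point holds as a minor inconsistency. SAP 15.3 would misclassify any malignancy recorded only on a CE page, and would do so in one direction: fewer serious events. The number of such malignancies is unknown and may be zero. The effect is at most about 0.09 percentage points per subject in the total column, and 0.50 to 0.11 points in a treatment group of 200 to 900 (assumed sizes). The analyses are descriptive, with no planned inference.

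A reader might go further and infer that malignancies have been dropped from the safety results, or that the primary SADR endpoint is understated. The documents support neither. No CE-only case is reported, all-event totals keep any such event, and SADR also requires a recorded relationship.

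The conclusion rests on reading the protocol's malignancy rule as fixing seriousness, and on the non-visible SAP text containing no rule that already deals with this.

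**What to change.** 1. Before database lock, take the CE events that are on the adjudicated malignancy list of SAP 15.5.2. Do not use the whole SMQ, which also contains unspecified tumours. Reconcile and de-duplicate these events against the AE dataset and the SAE reports. Query any without a match, and use the seriousness and relationship recorded in the matched source.
2. Amend SAP 15.3 along these lines: a CE event on the adjudicated malignancy list that still has no seriousness value after reconciliation is counted as serious, per protocol 8.5.1.3, in the SAE tables and in the serious rows of the Neoplasms SOC and AESI Malignancies summaries; it enters SADR only if a probable or possible relationship is recorded.
3. Footnote those tables with the number of CE-only malignancies, including zero, and how many lack a relationship assessment.
4. Leave the rule for all other CE events unchanged.

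The cost is a small reconciliation against reports the sponsor should already hold, one derivation rule and one footnote. Serious counts may rise slightly. If no CE-only malignancy exists, the counts stay as they are and the footnote says so.
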